[figure not shown]
[figure not shown]
[figure not shown]
[figure not shown]

Clinical Trial Protocol

Doc. No.: c01945509-06

BI Trial No.:	1245.29
BI Investigational Product:	Empagliflozin
Title:	A randomised, double-blind, placebo-controlled, parallel group, efficacy and safety study of empagliflozin (10 mg, 25 mg) administered orally, once daily over 24 weeks in hypertensive black/African American patients with type 2 diabetes mellitus
Clinical Phase:	IIIb
Trial Clinical Monitor:	 Tel:  Fax: 
Co-ordinating Investigator:	 Phone:  Fax: 
Status:	Final Revised Protocol (based on global amendment 4)
Version and Date:	Version: 5.0 Date: 18 July 2016
Page 1 of 144	
Proprietary confidential information. © 2016 Boehringer Ingelheim International GmbH or one or more of its affiliated companies. All rights reserved. This document may not - in full or in part - be passed on, reproduced, published or otherwise used without prior written permission.	

CLINICAL TRIAL PROTOCOL SYNOPSIS

Name of company: Boehringer Ingelheim		Tabulated Trial Protocol	
Name of finished product: NA			
Name of active ingredient: Empagliflozin			
Protocol date: 15Apr2014	Trial number: 1245.29		Revision date: 18 July 2016
Title of trial:	A randomised, double-blind, placebo-controlled, parallel group, efficacy and safety study of empagliflozin (10 mg, 25 mg) administered orally, once daily over 24 weeks in hypertensive black/African American patients with type 2 diabetes mellitus		
Co-ordinating Investigator:			
Trial sites	Multi-centre trial		
Clinical phase:	IIIb		
Objectives:	The objective of the current study is to investigate the efficacy and safety of empagliflozin (10 mg or 25 mg) compared to placebo on glucose control over 24 weeks in hypertensive black/African American patients with Type 2 Diabetes Mellitus (T2DM). A second objective of the study is to investigate the efficacy and safety of empagliflozin (10 mg or 25 mg) compared to placebo on BP over 12 weeks and on weight at 24 weeks in the same patient population. The study is designed to show superiority of empagliflozin over placebo.		
Methodology:	Randomised, double-blind, placebo-controlled, parallel group comparison		
No. of patients:	
total entered: 154 randomised hypertensive black/African American patients with type 2 diabetes mellitus (T2DM)
 
each treatment: 77 patients on empagliflozin 10 mg/25 mg 77 patients on placebo
		
Diagnosis :	T2DM and hypertension		

Proprietary confidential information.

© 2016 Boehringer Ingelheim International GmbH or one or more of its affiliated companies. All rights reserved.

This document may not - in full or in part - be passed on, reproduced, published or otherwise used without prior written permission.

Name of company: Boehringer Ingelheim		Tabulated Trial Protocol	
Name of finished product: NA			
Name of active ingredient: Empagliflozin			
Protocol date: 15Apr2014	Trial number: 1245.29		Revision date: 18 July 2016
Main criteria for inclusion:		
1. Diagnosis of T2DM prior to informed consent. Note: Documentation should be available before randomisation at latest. Confirmation can be in the form of formal documents or by verbal communication of the date of diagnosis from a patient or from their primary care physician (if records are not available). It is up to the medical judgment of the Investigator to deem if the information is accurate.
 
2. Male and female black/African American patients on diet and exercise regimen who are EITHER: drug-naïve (defined as absence of any oral antidiabetic therapy , glucagon like peptide-1 (GLP-1) analog or insulin for 12 weeks, 16 weeks for pioglitazone prior to randomisation), OR pre-treated with stable dose of metformin only, or sulfonylurea (SU) only, or DPP-4 inhibitor only, or metformin plus sulfonylurea, or metformin plus DPP-4 inhibitor. Treatment has to be unchanged for a minimum of 12 weeks prior to randomisation Dose for metformin: maximum tolerated dose The maximum daily dose of SU or DPP-4 inhibitor should not exceed that stated in the local label .
 
3. HbA1c of $\geq 7.0\%$ (53 mmol/mol) and $\leq 11.0\%$ (97 mmol/mol) at Visit 1 (screening)
 
4. Mean seated SBP 140-180 mmHg at Visit 1 (screening)
 
5. Successful completion of baseline ambulatory blood pressure (ABPM) testing with a mean systolic blood pressure (SBP) 135-175 mmHg prior to randomisation
 
6. Treatment with stable doses of at least one but no more than 4 antihypertensive medication ≥ 4 weeks prior to randomisation.
 
7. Age ≥ 18 years at Visit 1 (screening)
 
8. Signed and dated written informed consent by date of Visit 1 in accordance with Good Clinical Practice (GCP) and local legislation
	
Test product:		Empagliflozin	
dose:		10 mg / 25 mg, once daily	
mode of admin.:		Tablets per os	
Comparator product:		Placebo matching empagliflozin	
dose:		NA, once daily	
mode of admin.:		Tablets per p.o.	

Proprietary confidential information.

© 2016 Boehringer Ingelheim International GmbH or one or more of its affiliated companies. All rights reserved.

This document may not - in full or in part - be passed on, reproduced, published or otherwise used without prior written permission.

Name of company: Boehringer Ingelheim		Tabulated Trial Protocol	
Name of finished product: NA			
Name of active ingredient: Empagliflozin			
Protocol date: 15Apr2014	Trial number: 1245.29		Revision date: 18 July 2016
Duration of treatment: 
• 2 weeks placebo run-in• 24 weeks double-blind treatment with either empagliflozin 10 mg or empagliflozin 25 mg after dose escalation or placebo followed by two weeks follow up post study drug termination			

Proprietary confidential information.

© 2016 Boehringer Ingelheim International GmbH or one or more of its affiliated companies. All rights reserved.

This document may not - in full or in part - be passed on, reproduced, published or otherwise used without prior written permission.

Name of company: Boehringer Ingelheim		Tabulated Trial Protocol	
Name of finished product: NA			
Name of active ingredient: Empagliflozin			
Protocol date: 15Apr2014	Trial number: 1245.29		Revision date: 18 July 2016
Criteria for efficacy:	The primary endpoint in this study is change from baseline in HbA1c at 24 weeks of treatment.		
pharmacokinetics:	Key secondary endpoints are change from baseline in mean 24-hour ambulatory SBP at 12 weeks of treatment, change from baseline in mean trough ambulatory SBP at 12 weeks, change from baseline in body weight in kilograms (kg) at 24 weeks of treatment, and change from baseline in trough seated SBP at 12 weeks of treatment.		
pharmacodynamics:	Other secondary endpoints are described in Section 5.1.1 .		
Criteria for safety:	All adverse events including hypoglycaemic events and adverse events of special interest (AESI) and clinical laboratory values		

Proprietary confidential information.

© 2016 Boehringer Ingelheim International GmbH or one or more of its affiliated companies. All rights reserved.

This document may not - in full or in part - be passed on, reproduced, published or otherwise used without prior written permission.

Name of company: Boehringer Ingelheim		Tabulated Trial Protocol	
Name of finished product: NA			
Name of active ingredient: Empagliflozin			
Protocol date: 15Apr2014	Trial number: 1245.29		Revision date: 18 July 2016

Statistical methods:
 
For change from baseline in HbA1c up to 24 weeks of treatment a restricted maximum likelihood estimation based on a mixed-effect model for repeated measures analysis will be used to obtain adjusted means for the treatment effects on the full analysis set (FAS). This model will include treatment, visit, and the stratification factors renal function at baseline, and pretreatment with Metformin at screening as discrete fixed effects, baseline HbA1c as a continuous fixed effect, and interaction between visit and treatment, and an interaction between visit and baseline HbA1c. The primary treatment comparisons will be the contrast between treatments at the endpoint visit at 24 weeks of treatment.
 
For the change from baseline in trough seated SBP up to 12 weeks of treatment and the change from baseline in body weight in kg at 24 weeks as well a restricted maximum likelihood estimation based on mixed-effect models for repeated measures analysis will be used to obtain adjusted means for the treatment effects on the FAS. These models will include the same discrete fixed effects as the model for the primary endpoint and baseline HbA1c as continuous fixed effect, as well as interaction between visit and treatment, and interaction between visit and baseline measurement of the key secondary endpoint, as well as the corresponding baseline measurements of the key secondary endpoint as continuous effect. The primary treatment comparisons will be the contrast between treatments at the 12 week visit for seated SBP and 24 week visit for body weight.
 
The key secondary endpoint change from baseline in 24-hour ambulatory SBP and change from mean trough ambulatory SBP at 12 weeks will be analyzed by using an analysis of covariance (ANCOVA) approach in the FAS with last observation carried forward (LOCF) for missing data. The model will include randomised treatment, renal function at baseline, pretreatment with Metformin at screening as discrete fixed effects and the baseline of the key secondary endpoint and HbA1c at baseline as continuous fixed effects.
 
The overall type I error across the hypotheses tests in the confirmatory analysis will be maintained at a level of $\alpha \leq 0.05$ using a hierarchical testing sequence. The sample size of 154 patients per group was derived (assuming n=64 per groups plus a 20% drop-out rate) based on the requirement that the comparisons of empagliflozin versus placebo with respect to the HbA1c, BP and body weight should have a power of at least 80% at the two-sided α level of 5%.
 
Explorative statistical models and descriptive statistics will be used for the other secondary endpoints and safety parameters.
			

Proprietary confidential information.

© 2016 Boehringer Ingelheim International GmbH or one or more of its affiliated companies. All rights reserved.

This document may not - in full or in part - be passed on, reproduced, published or otherwise used without prior written permission.

FLOW CHART

Trial Period	Screening	Placebo run-in period		Randomised period							PTD Premature Treatment Discontinuation only ^s	Follow-up period
		2.1	2.2 ^B	3	4	5.1 ^B	5.2	6 ^O	7.1 ^B	7.2		
Visit	1 ^A											8
Study week	-3	-2	-1		4	11	12	18	23	24		26
Study day	-21	-14	-7	1	29	78	85	127	162	169		183
Visit window (in days)	+/-7	-7	+7	na	-7/+3	+7	-7/+7	+/-7	+14	+7		+7
Informed Consent	X											
Medical history / concomitant diagnoses	X											
Demographics	X ^H	X										
In-/Exclusion criteria	X	X		X								
Physical examination		X							X	X		
Vital signs	X	X		X	X		X		X	X		X
				X			X		X	X		X
Height	X											
Weight	X			X	X		X		X	X		X
				X			X		X	X		
Diet and exercise counselling ^C		X ^C		X ^C	X ^C		X ^C		X ^C	X ^C		X ^C
Food intake booklet completion		X ^R		X	X		X		X	X		X
12-lead ECG ^D	X											
Pregnancy test ^E	X			X	X		X		X	X		
Safety lab tests ^F (urine and blood)	X ^G	X		X	X		X		X	X		X
FPG sample		X		X	X		X		X	X		X
HbA1c	X			X	X		X		X	X		
Lipid lab panel				X			X		X	X		X
				X			X		X	X		
ABPM device attachment and removal ^I			X			X			X			

Proprietary confidential information.

© 2016 Boehringer Ingelheim International GmbH or one or more of its affiliated companies. All rights reserved.

This document may not - in full or in part - be passed on, reproduced, published or otherwise used without prior written permission.

Trial Period	Screening	Placebo run-in period		Randomised period							PTD Premature Treatment Discontinuation only ^S	Follow-up period
		2.1	2.2 ^B	3	4	5.1 ^B	5.2	6 ^O	7.1 ^B	7.2		
Visit	1 ^A	2.1	2.2 ^B	3	4	5.1 ^B	5.2	6 ^O	7.1 ^B	7.2		8
Study week	-3	-2	-1		4	11	12	18	23	24		26
				X								
Home Blood Glucose Monitoring ^L		X		X	X		X			X	X	X
Adverse events		X		X	X	X	X	X	X	X	X	X
Concomitant therapy	X	X		X	X		X	X		X	X	X
Dispense placebo run-in medication ^M		X										
Randomization (via an IRT system) ^Q				X								
Dispense study medication ^M				X	X		X					
Dose escalation ^N					X							
Medication compliance check				X	X		X			X	X	
Study medication termination										X	X	
Trial completion												X

A The screening procedures can be done on different days within the time window.

B Patients will undergo 24-hour ABPM testing. If patients fail the test, this procedure should be repeated. Each patient will be allowed a maximum of two attempts within the visit window to obtain one successful measurement starting at each of the ABPM time points (Visit 2.2, 5.1 and 7.1). If the ABPM testing is successful, procedures for the subsequent visit can be conducted on the same day after the ABPM device is removed and trough seated blood pressure measurement is taken.

Visit 2.2 ABPM and any repeat measurements if required should be performed during the run-in period within 7 days prior to Visit 3 (Day 1). Day 1 is the day of randomisation, not the day ABPM is applied.

Visit 5.1 ABPM and any repeat measurements if required should be performed within 7 days prior to Visit 5.2 (Day 85).

Visit 7.1 ABPM and any repeat measurements if required should be performed within 7 days prior to Visit 7.2 (Day 169). dx

C Diligent diet and exercise counselling by a diet specialist or trained staff member at visit 2.1. Counselling is based on local diet recommendations and should include a food log (recording of food intake for 3 consecutive days in the week before the actual visit). At all visits, patients should be reminded about the importance to follow the recommended diet and exercise plan.

D In addition to the visit indicated, ECG should be recorded in case of respective cardiac symptoms (indicating rhythm disorders or cardiac ischemia).

Proprietary confidential information.

© 2016 Boehringer Ingelheim International GmbH or one or more of its affiliated companies. All rights reserved.

This document may not - in full or in part - be passed on, reproduced, published or otherwise used without prior written permission.

- E For female patients (local urine pregnancy test in women of child-bearing potential).
- F Fasting blood and urine samples to be collected, for central labs at each visit indicated (refer to Lab manual). A urine dipstick to be done locally; upon positive result at site for leukocyte esterase (WBC) or nitrites a midstream urine sample should be taken and sent for urine culture analysis (central lab).
- G For the screening Visit 1, laboratory tests only include liver transaminases, alkaline phosphatase, serum creatinine, TSH and urinalysis. Patients do not have to be fasting.
- H Only screening relevant demographics (gender, date of birth).
- I The ABPM **device** is attached on the mornings of Visit 2.2, 5.1 and 7.1 before medication intake for measuring ABPM. This also applies to visits for repeat ABPM testing if required. Patients must have a successful completion of V2.2 ABPM prior to randomisation. Do NOT contact IRT system or dispense randomised study drug until after a successful 24-hour ABPM is complete. If after two attempts a successful reading is not achieved at either Visit 5.1 or Visit 7.1, patients should continue with the next scheduled visit (Visit 5.2/Day 85 or Visit 7.2/Day 169 respectively).
In case the ABPM must be repeated, the patient should continue taking trial medication. If possible, ABPM should take place within the visit window in the [Flowchart](#). If two doses of study medication are taken when the monitor is attached, then the ABPM should be repeated.

At the conclusion of each attempt, patient should be allowed to rest for at least 15 minutes after removal of the ABPM and a trough seated blood pressure measurement should be taken prior to intake of study medication.

- L Instruction and handover of device at Visit 2.1. Daily measurements during Run-in and Follow-up should be performed. During the treatment period, a weekly test is recommended. During the whole trial participation, additional measurements should be done in case of hypo- or hyperglycemia related symptoms.
- M At all visits the respective kit number has to be allocated to the patient via an interactive response technologies (IRT) system. All visit activities must be completed before contacting IRT.
- N At Visit 4 all patients will be dose escalated through an IRT system.
- O Visit 6 will be conducted as a phone visit.

- Q All visit activities must be completed and continued eligibility for randomisation or dosing confirmed prior to using IRT.
- R At Visit 2.1 the food log is dispensed only and to be completed for three consecutive days prior to Visit 3.

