3.3.6 Repeat test

HbA1c test (Visit 1) may be repeated once if the test result from the central lab is exclusionary but the most recent test result from a local lab (taken before Visit 1 but not older than one month), if any, falls within the acceptable range.

ABPM test (Visit 2.2) may be repeated once if the first attempt is unsuccessful. Refer to Footnote B and Footnote I of the [Flow Chart](#), as well as [Section 5.1.2](#) and [Section 6.2.1](#) for additional details on repeat ABPM.

Rationale for all repeat tests must be documented in source documents.

Proprietary confidential information.

© 2016 Boehringer Ingelheim International GmbH or one or more of its affiliated companies. All rights reserved.

This document may not - in full or in part - be passed on, reproduced, published or otherwise used without prior written permission.

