7. STATISTICAL METHODS AND DETERMINATION OF SAMPLE SIZE

7.1 STATISTICAL DESIGN - MODEL

This is a multi-centre, multi-national, randomised, parallel-group, double-blind, placebo-controlled trial to investigate the effect of (10 mg/25 mg) of empagliflozin and placebo after 24 weeks treatment on glucose control, BP and body weight in hypertensive black/African American patients with T2DM. The randomisation will be performed stratified by screening HbA1c values ($<8.5\%$, $\geq 8.5\%$), renal function at screening ($\text{eGFR} \geq 120 \text{ ml/min/1.73m}^2$, $\text{eGFR} 120\text{-}60 \text{ ml/min/1.73m}^2$, $\text{eGFR} \leq 60 \text{ ml/min/1.73m}^2$) and pretreatment with Metformin at screening (yes/no).

Based on experiences with the primary endpoints in other trials and based on literature data, the HbA1c change from baseline, and change from baseline in BP are regarded as normally distributed. Therefore, a restricted maximum likelihood estimation based on mixed-effect model for repeated measures analysis or an analysis of covariance (ANCOVA) approach can be used.

With regard to efficacy and safety endpoints, the term "baseline" refers to the last observed measurement prior to administration of any randomised study medication.

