7.2 NULL AND ALTERNATIVE HYPOTHESES

Primary Hypotheses

The confirmatory analyses will compare empagliflozin to placebo. The following hierarchical multiple testing procedure will be used to evaluate superiority for the primary endpoint followed by the evaluation of superiority of the key secondary endpoints, while maintaining the overall probability of a type I error at 0.05. The primary endpoint of change from baseline to 24 weeks in HbA1c along with the key secondary endpoints change from baseline in mean 24-hour ambulatory SBP at 12 weeks of treatment, change from baseline in mean trough ambulatory SBP at 12 weeks of treatment, change from baseline in body weight in kg at week 24 of treatment, and change from baseline in trough seated SBP at 12 weeks of treatment, will be tested in the following pre-specified hierarchical sequence, to address issues of multiplicity. Proceeding onto the next step in the sequence relies upon rejecting H_0 in the previous step, a 'success'. Each step will only be considered confirmatory if all previous steps were 'successful'. If any of the previous steps were not successful, the tests of the subsequent steps have to be interpreted in an exploratory sense. This procedure allows testing each step at the two-sided alpha-level of 5%:

1. change from baseline in HbA1c at 24 weeks of treatment
2. change from baseline in mean 24-hour ambulatory SBP at 12 weeks of treatment
3. change from baseline in mean trough ambulatory SBP at 12 weeks of treatment
4. change from baseline in body weight in kg at week 24 of treatment
5. change from baseline in trough seated SBP at 12 weeks of treatment

Proprietary confidential information.

© 2016 Boehringer Ingelheim International GmbH or one or more of its affiliated companies. All rights reserved.

This document may not - in full or in part - be passed on, reproduced, published or otherwise used without prior written permission.

At each of the 5 stages of the hierarchical sequence the hypotheses will be tested as described below:

$H_{0,1}$: No difference in mean endpoint between empagliflozin and placebo

$H_{1,1}$: A difference in mean endpoint between empagliflozin and placebo

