7.3.1 Primary analyses

Mean changes from baseline for HbA1c up to 24 weeks of treatment will be analyzed using a restricted maximum likelihood (REML)-based repeated measures approach on the FAS data set. Patients will be analysed according to the treatment group they are randomised to. Analyses will include the fixed, categorical effects of treatment, pre-treatment with Metformin at screening, renal function at baseline, visit, and treatment-by-visit interaction, as well as the continuous, fixed covariates of baseline HbA1c and baseline HbA1c -by-visit interaction. An unstructured (co)variance structure will be used to model the within patient measurements. If the model first fails to converge using an unstructured (co)variance structure, then a hierarchical approach is applied until a (co)variance structure is obtained where the model converges. Therefore the following (co)variance structures are tested according to the pre-specified order: (1) unstructured, (2) Toeplitz, (3) variance components, (4) compound symmetry. As soon as one model converges this will be the final model used, therefore no further testing of subsequent (co)variance structures is required. The Kenward-Roger approximation will be used to estimate denominator degrees of freedom. Significance tests will be based on least-squares means using a two-sided $\alpha = 0.05$ (two-sided 95%

Proprietary confidential information.

© 2016 Boehringer Ingelheim International GmbH or one or more of its affiliated companies. All rights reserved.

This document may not - in full or in part - be passed on, reproduced, published or otherwise used without prior written permission.

confidence intervals). The primary treatment comparisons will be the contrast between treatments at the endpoint visit at 24 weeks of treatment.

For the key secondary endpoint change from baseline in mean 24-hour ambulatory SBP at 12 weeks of treatment an ANCOVA comparing the change from baseline in mean 24-hour ambulatory SBP at 12 weeks of treatment will be used as primary analysis on the FAS using last observation carried forward (LOCF) for missing ABPM assessments.

The statistical model will be the following:

change from baseline in 24-hour ambulatory SBP at 12 weeks =

overall mean + baseline 24-hour ambulatory SBP + treatment + pre-treatment with Metformin + renal function + HbA1c + random error

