7.6 DETERMINATION OF SAMPLE SIZE

In order to ensure that each comparisons of empagliflozin and placebo with respect to HbA1c, mean systolic ABPM blood pressure and body weight have a power of at least 80%, 64 patients plus an additional 20% drop-out rate, resulting in 77 patients per arm are required per treatment group. This is derived from the assumption that the difference in change from baseline compared to placebo in 24-hour SBP is 5 mmHg with a standard deviation of 10

Proprietary confidential information.

© 2016 Boehringer Ingelheim International GmbH or one or more of its affiliated companies. All rights reserved.

This document may not - in full or in part - be passed on, reproduced, published or otherwise used without prior written permission.

mmHg (resulting in a power of 80%), and the difference in body weight is 2 kg with a standard deviation of 2.3kg (resulting in a power of 99%). With this sample size the power to detect a 0.6% difference in HbA1c with a standard deviation of 1.1% will be >85%.

The planned treatment group sizes are considered as sufficient for the confirmatory evaluation of efficacy and the descriptive assessment for safety, tolerability and PK.

Proprietary confidential information.

© 2016 Boehringer Ingelheim International GmbH or one or more of its affiliated companies. All rights reserved.

This document may not - in full or in part - be passed on, reproduced, published or otherwise used without prior written permission.

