This model includes effects accounting for the following sources of variation: ‘HbA_{1c} baseline’, ‘treatment’, ‘renal function’, ‘pretreatment with metformin’, ‘visit’, ‘visit by treatment interaction’ and ‘HbA_{1c} baseline by treatment interaction’. ‘Treatment’, ‘renal function’, ‘pretreatment with metformin’, ‘visit’ and ‘visit by treatment interaction’ are fixed classification effects, and ‘HbA_{1c} baseline’ is a linear covariate. The interaction ‘visit by HbA_{1c} baseline interaction’ will be based on the linear covariate ‘HbA_{1c} baseline’.

For each patient, the error terms from all the visits represent the within-patient variability, and are assumed to follow a multivariate normal distribution with an unstructured covariance matrix. If the model first fails to converge using an unstructured (co)variance structure, then a hierarchical approach is applied until a (co)variance structure is obtained where the model converges. Therefore the following (co)variance structures are tested according to the pre-specified order: [1] unstructured, [2] Toeplitz, [3] variance components, [4] compound symmetry. As soon as one model converges this will be the final model used, therefore no further testing of subsequent (co)variance structures is required.

The treatment effect will be estimated on the basis of the least square mean treatment difference at week 24 extracted from the primary analysis model.

[figure not shown]
The Kenward-Roger approximation will be used to estimate the denominator degrees of freedom. Significance tests will be based on least-squares means using a two-sided $\alpha = 0.05$ (two-sided 95% confidence intervals).

[figure not shown]

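### The primary HbA1c model leaves out screening HbA1c, a scheduled pre-treatment reading and a randomisation stratum; adding it could give a small gain in precision, possibly none

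*Protocol*

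**What the plan says.** The flow chart marks HbA1c at Visit 1 (day -21) and again at Visit 3 (day 1), and Protocol 5.1.2 sends the samples to the central laboratory. The Visit 1 result decides eligibility (7.0% to 11.0%, inclusion criterion 3). It also defines a stratum: "The randomisation will be performed stratified by screening HbA1c values", cut at 8.5% (Protocol 7.1 and 7.5). Under Protocol 3.3.6, "HbA1c test (Visit 1) may be repeated once if the test result from the central lab is exclusionary" and a recent local result lay within range.

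Baseline is the last measurement before any randomised drug (Protocol 7.1, SAP 6.7), so normally Visit 3.

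The primary model is the same in three places. The synopsis names renal function and then "pretreatment with Metformin at screening as discrete fixed effects, baseline HbA1c as a continuous fixed effect, and interaction between visit and treatment", followed by visit by baseline HbA1c. Protocol 7.3.1 lists the categorical effects "as well as the continuous, fixed covariates of baseline HbA1c and baseline HbA1c -by-visit interaction". SAP 7.4.1 gives the same equation and states that "The treatment effect will be estimated on the basis of the least square mean treatment difference at week 24". (One item in the SAP's list under its equation reads as baseline by treatment; the equation and the protocol have baseline by visit, which I take as the model.) Screening HbA1c is absent from all three, both as a continuous value and as its stratum. I found no reason for this in the readable text.

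**The concern.** A single HbA1c reading contains assay and short-term within-person variation. A second reading, taken about three weeks earlier and before randomisation, may hold further information on the week 24 value. If so, adjusting for it lowers the residual variance and narrows the interval for the primary contrast without new data. Because the value is fixed before randomisation, adjusting for it cannot bias the comparison. The plan also treats its stratification factors unevenly: renal function and metformin pretreatment are in the model and screening HbA1c is not.

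HbA1c is the first step of the fixed sequence. If it fails, the four key secondary tests become exploratory (Protocol 7.2), so precision here serves the whole confirmatory chain.

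**Working it through.** **Inputs from the documents.** Two-sided 5% (Protocol 7.2: "This procedure allows testing each step at the two-sided alpha-level of 5" per cent). Protocol 7.6: "With this sample size the power to detect a 0.6% difference in HbA1c with a standard deviation of 1.1% will be >85" per cent, and "64 patients plus an additional 20% drop-out rate, resulting in 77 patients per arm are required per treatment group".

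**Step 1, the plan's own figure.** With 64 per arm the standard error is 1.1 × √(2/64) = 0.1945, and 0.6 / 0.1945 = 3.086. With 126 degrees of freedom the critical value is 1.979, and the noncentral t distribution gives a power of 86.5% (normal approximation 87.0%). The stated figure reproduces.

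**Step 2, effect of a second covariate.** Let a = corr(Visit 3, week 24), b = corr(Visit 1, week 24) and ρ = corr(Visit 1, Visit 3). Then

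R² = (a² + b² − 2ρab) / (1 − ρ²), and the residual variance ratio = (1 − R²) / (1 − a²).

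The documents give none of these correlations, so the values below are assumptions. I apply the ratio to SD 1.1, read as the residual SD of the planned model; the protocol does not say whether 1.1 is raw or adjusted.

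Central case (ρ = 0.90, a = b = 0.6): R² = (0.72 − 0.648) / 0.19 = 0.3789; ratio = 0.6211 / 0.64 = 0.970; SD = 1.1 × √0.970 = 1.084.

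| ρ | a | b | variance change | power at 64 per arm (noncentral t) |
|---|---|---|---|---|
| 0.80 | 0.6 | 0.6 | −6.3% | 88.5% |
| 0.90 | 0.6 | 0.6 | −3.0% | 87.5% |
| 0.95 | 0.6 | 0.6 | −1.4% | 87.0% |
| 0.90 | 0.6 | 0.57 | −0.7% | 86.7% |
| 0.90 | 0.6 | 0.54 (= ρ × a) | 0% | 86.5% |

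In patients, the central case is worth about 2 per arm (64 / 0.970 = 66.0) and the first row about 4 (64 / 0.9375 = 68.3). On the normal approximation the first row gives 89.0%, starting from 87.0%.

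The most favourable corner examined, ρ = 0.80 with a = b = 0.7, gives −10.7%. If the two readings are equal, independent-error measures of one true value, this needs a correlation of true baseline with week 24 of 0.7 / √0.80 = 0.78. I do not carry it into the main range.

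**Step 3, cross-check with a measurement-error model.** Let one reading have reliability r, the mean of two 2r/(1 + r), and let c be the correlation of true baseline with week 24. The ratio is (1 − c² × 2r/(1 + r)) / (1 − c²r).

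- r = 0.85, c = 0.7: ratio 0.942, power 88.4%
- r = 0.90, c = 0.6: ratio 0.975, power 87.3%
- r = 0.95, c = 0.6: ratio 0.987, power 86.9%
- r = 0.95, c = 0.4: ratio 0.995, power 86.6%

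**Step 4, the entry window and the cost of the extra term.** A two-arm ANCOVA at week 24 was simulated with 64 per arm and Visit 1 values restricted to 7-11%. With a = b = 0.6 the estimated variance ratio was 0.959, 0.982 and 0.995 for ρ = 0.80, 0.90 and 0.95. When Visit 1 added nothing beyond Visit 3 it was about 1.01, a loss of about 1% of variance (power about 86.1% in the Step 1 formula).

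**The case against.** The strongest reply is that this is a preference. The model already adjusts for continuous pre-treatment HbA1c and its interaction with visit, the test is valid, and the stated power is reached. That stands.

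The gain may also be nil. Diet and exercise counselling and the placebo run-in come between the two samples. Visit 1 values are selected by the entry window, and some may be repeats of an exclusionary result. Visit 3 is closer to week 24. A Visit 1 correlation with week 24 only 5% lower than Visit 3's (0.57 against 0.6) cuts the central gain from 3.0% to 0.7%. That stands too, and the range has to start at zero.

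The sample size is driven by 24-hour SBP (5 mmHg, SD 10 mmHg, 80.1% recomputed), the second step of the sequence. One or two points of power on HbA1c do not move that limit.

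A reader might infer more than the documents support:

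- *Every randomised patient has two values.* This holds by schedule only. If the Visit 3 sample is missed, Visit 1 becomes the baseline. The SAP also foresees a missing baseline HbA1c (violation E.01).
- *Error in the Visit 3 value harms the test because the endpoint is change from it.* With baseline and its visit interaction in the model, change and week 24 value give the same treatment contrast.
- *Chance imbalance in HbA1c is uncontrolled.* Screening HbA1c is balanced by stratification and the last pre-dose value is a covariate.
- *A numeric Visit 1 HbA1c is held in the IRT.* The documents name only the two strata.

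The objection does not answer why one stratification variable of three, already collected, is left out without a stated reason.

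**Conclusion.** The point holds as a minor, optional improvement. Visit 1 HbA1c is a pre-randomisation value that the trial collects and stratifies on, and the primary model does not use it. Under assumed correlations (Visit 1 with Visit 3 0.80-0.95; Visit 3 with week 24 about 0.6; Visit 1 with week 24 from equal to that down to no added information), the residual variance falls by 0% to about 6%. Power at 64 per arm then lies between 86.5% and about 88-89%. The downside is about 1% of variance. The size cannot be taken from the documents, and the gain is likely to be small.

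A reader might conclude that the primary analysis is invalid or underpowered because a stratification factor is missing. The documents do not support that: the comparison is randomised, a continuous HbA1c covariate is in the model, and the stated power reproduces without the change.

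**What to change.** Before unblinding, in the synopsis, Protocol 7.3.1 and SAP 7.4.1, add continuous Visit 1 (screening) HbA1c and its interaction with visit to the primary MMRM, next to baseline HbA1c. Add Visit 1 HbA1c to the supportive HbA1c ANCOVA in Protocol 7.3.2. Keep the endpoint as change from the last pre-dose value, and keep the baseline definition.

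State two rules with it. If the Visit 1 test was repeated, use the central-laboratory result on which eligibility and the randomisation stratum were based. If the Visit 3 sample is missing, the Visit 1 value serves as both covariates.

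The cost is a few degrees of freedom in about 154 patients and one line of model code. The text changes in three places for the primary model and one for the ANCOVA. As this alters a confirmatory model, record it in SAP Section 4. If the sponsor prefers the present model, one sentence saying why screening HbA1c is left out would be enough.
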